The objectives of this pilot randomized controlled trial are to (1) determine the feasibility and acceptability of study procedures (recruitment, randomization, and data and sample collection) and CSM-IBD; (2) compare CSM-IBD to usual care on changes from baseline to 3 months post intervention in quality of life and daily symptoms (fatigue, sleep disturbance, psychological distress, gastrointestinal symptoms) among IBD patients and (3) explore the association of socioecological factors (age, sex, race, ethnicity, or diet), clinical phenotype (medications, disease distribution, and disease activity), and biological signatures (microbiome and calprotectin) with symptoms at baseline and response to intervention (post intervention).

Methods

Study Design

The proposed study is a 2-arm pilot randomized controlled trial that follows the Consolidated Standards of Reporting Trials and Standard Protocol Items: Recommendations for Interventional Trials guidelines [30,31]. In a 2:1 ratio, 54 participants will be randomized (intervention=36 participants; usual care=18 participants). This randomization scheme was selected to maximize data collection and information regarding the intervention group. The intervention will take place over 8 sessions. The participants will be blinded to the study hypotheses. Web-based self-reported questionnaires will be used to reduce detection bias.

Theoretical Framework

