Participants are individuals seeking care for their IBD at the University of Washington (UW). Inclusion criteria include participants who (1) have a health care provider diagnosis of IBD as reported in the electronic medical record, (2) report at least 2 current, active symptoms (Short Inflammatory Bowel Disease Questionnaire [SIBDQ] equal or less than 4 [“some of the time”] on any 2 items), (3) are 18 to 75 years old, and (4) are able to read and write in English.

Participant exclusion criteria include (1) pregnant individuals, (2) significant co-occurring mental or physical conditions that would impact study participation, (3) surgery or hospitalization within the past month, or (4) living outside of Washington State.

CSM Intervention

The 8-session CSM includes patient education about self-management of symptoms using CBT, relaxation training, and diet counseling. The intervention will be delivered digitally with skill videos, readings, and homework, as well as a weekly phone call or Zoom check-in with a nurse trained in CBT. For each session, participants will review information and practice skills on the session topic. The content for each session is outlined in [Table 2](#). The weekly phone calls are designed to provide accountability and support for achieving the session goals and to enable individuals to ask questions about the content. The estimated time of completion is 8 weeks; however, participants will have 12 weeks to complete the sessions to allow for unexpected events. Intervention fidelity will be monitored using fidelity checklists and through the evaluation of a random selection of 20% of participants.

Also of note, the original CSM intervention was administered as a paper workbook with weekly hour-long sessions with a trained advanced practice nurse. To improve accessibility and feasibility, we have adapted the intervention to be administered as a web-based intervention with weekly phone call check-ins with a CBT-trained nurse. This unique approach expands the feasibility and reach of the intervention by enabling patients who may live in rural or underserved areas to access the intervention content. To be appropriate for the IBD population, the session 1 disease content was modified to include the role of inflammation, the importance of endoscopic remission, and information on when to contact their health care provider. The intervention content was reviewed by patients and health care providers.

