2. Biological signatures: stool samples will be collected by participants and stored immediately in home freezers (-20°C) before transport to the UW School of Nursing Biobehavioral Laboratory. Samples will be stored at -80°C until batch processing.
 - Gut microbiome: fecal microbial communities will be characterized using metagenomic shotgun sequencing on the Illumina MiniSeq or NextSeq platforms (Illumina, Inc) [46,47].
 - Fecal calprotectin: fecal calprotectin is a biomarker used to measure inflammation in the gut and will be assessed using an enzyme-linked immunosorbent assay [48].
3. Socioecological factors were selected based on the National Institute for Nursing Research's common data elements and include sex, gender, age, race or ethnicity, education level, employment, marital or partner status, household size, and neighborhood (urban or rural, zip code). Dietary intake can influence the composition of the gut microbiome and symptoms [49]. At the time of the stool collection, subjects will complete a detailed 3-day food record (Fred Hutchinson Cancer Research Center Nutrition Assessment).
4. The clinical phenotype will be obtained from the electronic medical record: type of disease, time since diagnosis, history of bowel surgery, disease distribution (measured by

the Montreal Classification), medications, and disease activity (Harvey Bradshaw Index for Crohn Disease [50] and Simple Colitis Activity Index for Ulcerative Colitis [51]; <5 indicates remission).

5. Health care use will be evaluated from the electronic medical record and patient self-report, including emergency department use, hospitalizations, outpatient visits, laboratory tests, imaging, and procedures, as well as providers' nonclinical time spent managing patients.

Participant Timeline

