All procedures will occur remotely; data collection will occur digitally through REDCap (Research Electronic Data Capture; Vanderbilt University), a secure Health Insurance Portability and Accountability Act (HIPAA)-compliant database [52,53]. Individuals meeting eligibility criteria and interested in the study will be asked to sign a consent form and HIPAA form prior to participating in the study. All participants will complete baseline questionnaires (socioecological factors and disease information). Participants will collect a stool sample at home using a stool sample collection kit (instructions and researcher contact information will be provided); a 3-day food record will be collected starting 2 days before the stool sample collection. The stool samples will be placed in home freezers and returned to the School of Nursing Biobehavioral Laboratory. Participants will be provided with ice packs, a Styrofoam mailing box, and return labels. Stool samples will be stored at -80°C until batch processing.

Following baseline data collection, participants will be randomly assigned to the 8-session CSM-IBD or usual care. Immediately post intervention, participants will complete questionnaires, collect a stool sample, and report a 3-day food record. Three months post intervention, participants will complete questionnaires and participate in a qualitative data collection interview. In addition, participants will report whether or not they are continuing the self-management skills learned in the intervention. Semistructured interviews will be conducted to understand the participants' perspective on procedural burden and suggestions to improve the intervention, including satisfaction with the intervention. Interviews will be recorded and transcribed. Participants will be compensated for each assessment completed (baseline, immediately post intervention, and 3 months post intervention). To increase retention, participants in the usual care group will be provided access to the intervention upon study completion. Participants can continue the study despite not completing all data collection assessments and all intervention sessions.

Sample Size

Based on recommendations for preliminary studies [54], we aim for data on 54 participants (36 intervention and 18 usual care). The sample size is appropriate for assessing feasibility and acceptability (aim 1). For aim 2, we will be able to detect fairly large effect sizes of 0.81 with

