80% power. For aim 3, there will be 80% power to detect a correlation of 0.45. As a pilot study, the project is not powered to detect differences or correlations unless they are large.

Recruitment

Overview

Participant recruitment will take place at the UW Inflammatory Bowel Disease Clinics. The UW sees a large number of patients with IBD and serves as a tertiary care clinic for patients with IBD in the Washington, Oregon, Alaska, Montana, and Idaho regions. Recruitment may occur in three different settings: (1) in a clinic, (2) virtually (via telephone, email, or mail), and (3) by posting on the Institute of Translational Health Sciences website. All individuals will be informed that participating or not participating will not influence the care that they receive.

In a Clinic

Weekly prescreening will occur to determine if participants with scheduled IBD clinic appointments may be eligible for the study. The goal of prescreening is to enable purposeful sampling of patients based on demographic (eg, age and race) and disease characteristics (eg, disease activity). Individuals who are eligible will receive a flyer containing the study purpose and contact information from either their health care provider or study staff (depending on feasibility and current COVID-19 restrictions). Individuals will have time to review the study information. Participants can call study staff or complete a REDCap survey to express their interest and complete screening questions.

Virtually

The team may contact potential participants via phone, email, or mail if in-person recruitment becomes difficult or not feasible. All contact will follow the UW's institutional review board guidelines for cold contact recruitment. Those expressing interest in the study will call study staff for more information and then complete additional screening questions.

Institute of Translational Health Sciences Website

Information regarding the study will be posted on the UW Institute of Translational Health Sciences website. Interested individuals can complete the contact form to be contacted by study staff and can complete screening questions digitally.

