Analyses of microbiome data will use 3 summary measures—Shannon diversity, richness, and *Firmicutes/Bacteroidetes* ratio—as well as the relative abundance of bacterial families (eg, family Ruminococcaceae) and genera and will control for the read count. For diet, we will focus on protein and fiber intake, as our previous work has indicated these may be important dietary intake components related to the gut microbiome. First, we will examine the associations between socioecological, clinical phenotype, and biological signatures with symptoms at baseline in the total sample using Pearson correlation or Spearman rank correlation based on measure distributions. Scatter plots will be used to visually display these associations. Second, we will examine associations between socioecological, clinical phenotypes, and biological signatures at baseline and response to intervention in the intervention group. Response to intervention is conceptualized as an increase of 8 points on the SIBDQ scale (quality of life) [40] or a 50% decrease from baseline in the GI symptom score [27]. Among the intervention group, we will use the *t* test and chi-square test to compare socioecological factors, clinical phenotypes, and biological signatures among patients with and without a response to treatment.

Monitoring

This study has been classified as a minimal-risk study. The principal investigator has the responsibility for study oversight, including patient safety and data quality, as well as submitting reports to the funder and the institutional review board. Due to the low-risk nature of the CSM-IBD, we do not anticipate any adverse events or serious adverse events. The data safety and monitoring team will meet quarterly to review the study. The team will monitor accrual, withdrawals, data quality, timeliness of data submission, protocol compliance, and the types and frequency of adverse events and serious adverse events. No interim analysis or stopping rules are currently planned. However, if any adverse events or serious adverse events are reported, the data safety and monitoring team will meet within a week to discuss the event and any potential changes needed to the study procedures.

Ethics and Dissemination

Data Management

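### Disease activity is scored on a different index in each disease, but the aim 3 analyses pool the diseases with no disease-type term and do not say whether the raw score or remission status is used

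*Combined protocol and SAP*

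**What the plan says.** - **Measurement.** Study Outcomes, Secondary Outcomes, item 4 gives the activity measure as "Harvey Bradshaw Index for Crohn Disease [50] and Simple Colitis Activity Index for Ulcerative Colitis [51]; <5 indicates remission". The same item records which disease each participant has: "The clinical phenotype will be obtained from the electronic medical record: type of disease, time since diagnosis".
- **Role.** The third objective lists "clinical phenotype (medications, disease distribution, and disease activity" among the factors to be explored.
- **Who enters.** Study Population admits anyone who meets "have a health care provider diagnosis of IBD as reported in the electronic medical record". Both diseases are therefore eligible, and no Crohn/ulcerative colitis split is planned.
- **Baseline analysis.** Statistical Analysis, Secondary Outcomes relates the socioecological, clinical phenotype and biological variables "with symptoms at baseline in the total sample using Pearson correlation or Spearman rank correlation based on measure distributions".
- **Responder analysis.** The same section compares these variables between responders and non-responders in the intervention group by t test and chi-square test.
- **What is absent.** Neither analysis has a disease-type term, a stratum or any within-index scaling. The form in which disease activity enters is not stated. No range, mean or SD is given for either index.

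**The concern.** A shared remission threshold aligns one point on two scales. It does not make the rest of the scores exchangeable: a given score on one index need not mean the same as that score on the other, and the means and spreads may differ. If raw scores are pooled, part of the variation in the activity variable reflects which instrument was used.

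There are two consequences. If mean symptoms are the same in both diseases, the instrument difference is noise and the coefficient shrinks. If mean symptoms also differ, the instrument difference is confounded with disease, and the coefficient can move either way, including away from zero where neither disease shows an association.

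The responder comparison has the same weakness. With raw scores, the difference in mean activity between responders and non-responders contains a component equal to the offset between the indices times the difference in disease mix between those two groups.

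At stake is how one of the three clinical factors named in the third objective is read when the full-scale trial is designed.

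**Working it through.** **1. The plan's own figure.** Sample Size says of aim 3 that "there will be 80% power to detect a correlation of 0.45". No alpha is given there; I assume two-sided 0.05. By Fisher's z:

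- n = ((1.960 + 0.842) / atanh 0.45)² + 3 = (2.802 / 0.4847)² + 3 = 36.4.
- Power at n = 36: Φ(0.4847 × √33 − 1.960) = 79.5%.
- Power at n = 54: Φ(0.4847 × √51 − 1.960) = 93.3%. The detectable r at 80% power is tanh(2.802/√51) = 0.373.

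The figure reproduces at the size of the intervention group (36), not at the total sample of 54 used for the baseline correlations. The plan should say which n it means, but the scale question does not depend on this.

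**2. Effect of pooling raw scores.** Every input here is an assumption: a 1:1 disease mix, equal within-disease spread, a common within-disease correlation r, index means dx SD apart and symptom means dy SD apart. Then

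pooled r = (r + dx·dy/4) / √[(1 + dx²/4)(1 + dy²/4)]

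| r | dx | dy = −0.5 | dy = 0 | dy = +0.5 |
|---|---|---|---|---|
| 0.50 | 0.5 | 0.41 | 0.49 | 0.53 |
| 0.50 | 1.0 | 0.33 | 0.45 | 0.54 |
| 0.50 | 1.5 | 0.24 | 0.40 | 0.53 |
| 0 | 0.5 | −0.06 | 0 | 0.06 |
| 0 | 1.0 | −0.11 | 0 | 0.11 |
| 0 | 1.5 | −0.15 | 0 | 0.15 |

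Worked cell: r = 0.50, dx = 1.5, dy = −0.5 gives (0.50 − 0.1875) / √(1.5625 × 1.0625) = 0.3125 / 1.2885 = 0.24.

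**3. Unequal spread and the plan's r of 0.45.** Now let the second index have an SD between 1 and 0.5 times that of the first, with dx from 0 to 1 and dy from −0.5 to +0.5. A within-disease r of 0.45 becomes a pooled r between 0.22 and 0.50, and power at n = 54 runs from 36% to 97%. A within-disease r of 0 becomes −0.13 to +0.13, with simulated type I error up to about 16%. With dy = 0 the type I error stays near 5%.

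**4. Does Spearman help?** No. In the simulated case with dx = 1, SD ratio 0.5 and dy = −0.5, Pearson averages 0.22 with 35% power and Spearman 0.20 with 32%. Ranks taken across two instruments inherit the same offset.

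**5. What restores the association.** A disease-type term alone removes the difference in means but not the difference in spread. With an SD ratio of 0.5 and no mean differences, r = 0.45 becomes (0.5 × 0.45 + 0.5 × 0.45 × 0.5) / √(0.5 + 0.5 × 0.25) = 0.3375 / 0.7906 = 0.43. Standardising the index alone leaves any symptom difference in place: 0.50 / √1.0625 = 0.485 at dy = 0.5. Doing both handles each part. In simulation, within-disease standardisation returns a mean r of 0.445 and 93% power.

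**6. Cost in power.** One disease-type term at n = 54 moves the detectable r from 0.373 to tanh(2.802/√50) = 0.377. Power at r = 0.45 goes from 93.3% to 92.9%. Estimating within two strata and combining gives a detectable r of 0.384 and 91.9% power.

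**The case against.** The strongest reply is that the plan never commits to a raw pooled score. The analysis section names blocks of variables, and the clinical phenotype block includes medications, disease distribution and disease type, which cannot all be raw Pearson inputs. The only use of the indices that the documents state is a remission threshold, and a remission variable would go to the chi-square test in the responder step. This stands: a reader might infer that a raw-score correlation, or a t test alone, is prescribed, and the text does not say so. It does not dispose of the point. The raw form is equally open, and the binary form reduces the problem without clearly removing it, because one cut-off on two instruments need not mark the same state in both diseases.

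Second, the size is hypothetical. No score distributions, disease mix or symptom levels by disease are given, and nothing anchors an offset as large as 1.5 SD. A reader might infer that a false association is to be expected. The illustration does not support that: it needs a symptom difference as well, and even then reaches only about ±0.15, against a two-sided 5% critical value of about 0.27 at n = 54.

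Third, if one disease truly is both more active and more symptomatic, that contrast is information, and within-index scaling removes it. This is fair as a matter of estimand, but raw scores from two instruments cannot separate a true difference in activity from a difference of scale.

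Fourth, a reader might extend the request to every total-sample association. The documents do not support that: the scale problem has been shown only for disease activity, and adjusting disease type for itself is impossible.

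**Conclusion.** The point holds for disease activity alone, and conditionally. Two indices, analyses that combine the diseases, and no disease-type term are all in the text. The omitted form of the variable is a gap in itself. If raw scores are used, the pooled coefficient is attenuated when mean symptoms are equal across the diseases, and can be biased in either direction when they differ.

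The size cannot be derived from the documents. Under the equal-spread assumptions of step 2, a within-disease r of 0.50 reads as 0.40 to 0.49 with equal mean symptoms, and as 0.24 to 0.54 with a 0.5 SD symptom difference. With that same symptom difference, a true r of 0 reads as at most about ±0.15. The real distortion may be smaller.

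This is an exploratory aim of a pilot study. The primary outcomes, allocation and sample size do not depend on it. The change is worth making because a better analysis is available from data already collected, at almost no cost.

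**What to change.** In Statistical Analysis, Secondary Outcomes, for disease activity only:

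1. State whether it enters as the raw index score or as remission versus active.
2. If it is the raw score, standardise it within index and include disease type, by partial correlation or regression for the baseline association and by an adjusted model for the responder comparison. Estimating within each disease and combining is an acceptable alternative.
3. If it is remission versus active, adjust both analyses for disease type.
4. Do not make a raw pooled coefficient the main estimate. Per-disease estimates can be shown descriptively; on their own they are imprecise (detectable r about 0.52 in each disease for an assumed 27/27 split).

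The cost is a few sentences of analysis text and about one degree of freedom. Disease type is already collected, so data collection, recruitment and sample size do not change.

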In all instances, the purpose of the study, study design, and length of time to complete the study will be discussed. To assess participants' understanding of study procedures, individuals will be asked to briefly describe the study. Interested individuals will complete additional screening questions to confirm whether patients meet the specified inclusion and exclusion criteria.

Screening questionnaires may be completed over the phone or electronically via REDCap, based on patient preference. Those meeting inclusion or exclusion criteria will be invited to participate in the study, sign a consent form, and begin data collection. Throughout the entire process of

informed consent, from the first contact with the patient, the potential participants are able to ask any questions or delay making a decision. This screening and recruitment process will continue until the target sample size has been reached.

Intervention Allocation

A computer adaptive randomization procedure using a modification of the minimization method proposed by Pocock and Simon [55] will be used to balance groups based on SIBDQ at baseline. Once the data are entered into the computer, the computer program will return the participants' group assignment.

Statistical Analysis

Feasibility

The number and percentage will be calculated for participants who were prescreened, approached, screened, and enrolled (recruitment). We will assess dropout rates between the CSM-IBD and usual care (randomization). Quality of data will focus on the data completeness of questionnaires; missing data will be reported, and bivariate comparisons will be made between individuals with and those without missing data (data collection). We will report how many participants collected biological samples within the desired timeframe (sample collection). The mean and SD will be reported for the Feasibility of Intervention Measure (intervention feasibility).

Acceptability

Transcripts from participant interviews will be coded by 2 individuals using open coding methods (acceptability and satisfaction). In addition, numbers and percentages will be reported for participants who continue to use self-management strategies 3 months post intervention.

Primary Outcomes

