Data from the 2 follow-up time points (immediate and 3 months post intervention) will be analyzed together using linear mixed models for each of the outcomes. For example, one model will have a change in the quality of life from baseline to immediate and 3 months post intervention as the outcomes, subject as a random effect, time (immediate or 3 months) as a within-subject fixed factor, and treatment group as an across-subject fixed factor. Baseline quality of life will be included as a covariate in the model, as will any baseline variables that differ between the 2 treatment groups. The parameter for the treatment group factor will provide an estimate of the treatment effect, that is, the difference between the treatment groups in mean change in the quality of life, and a 95% CI on the estimated difference will be computed. We hypothesize participants in the CSM-IBD will report a greater reduction in symptoms compared to those in usual care. A second model will also include an interaction between group and time to test whether the treatment effect is different at the 2 post intervention times. Additional analyses will estimate treatment effects separately for men and women.

Secondary Outcomes

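### Minimisation uses baseline SIBDQ alone although effects will be estimated separately for men and women, so the sex make-up of the 18-person usual-care arm is left to chance

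*Combined protocol and SAP*

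**What the plan says.** The Study Design section sets a 2:1 ratio: "54 participants will be randomized (intervention=36 participants; usual care=18 participants". Intervention Allocation states that "a modification of the minimization method proposed by Pocock and Simon [55] will be used to balance groups based on SIBDQ at baseline". The modification is not described, and neither sex nor disease type is mentioned there.

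Statistical Analysis, Primary Outcomes, fits linear mixed models to change from baseline. Baseline quality of life is a covariate, and so is any baseline variable found to differ between the arms; no criterion for differing is given. The section closes: "Additional analyses will estimate treatment effects separately for men and women".

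Crohn disease and ulcerative colitis are enrolled together. The clinical phenotype, listed under Secondary Outcomes, includes type of disease and "disease activity (Harvey Bradshaw Index for Crohn Disease [50] and Simple Colitis Activity Index for Ulcerative Colitis [51]; <5 indicates remission"). No treatment-effect analysis by disease type is planned.

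**The concern.** Minimisation is built to balance several factors at once. Here it is given one, the baseline value of an outcome that the model adjusts for anyway. Sex, the one factor by which treatment effects will be split, is left out, although it is collected with the baseline questionnaires before randomisation.

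What is at stake is the number of usual-care men and women. A covariate can adjust an overall comparison for an uneven split. It cannot supply control participants to a sex-specific comparison that has too few.

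**Working it through.** **Inputs.** 36 v 18 participants (Study Design); detectable effect 0.81 at 80% power (Sample Size). Two-sided 5% is assumed, in line with the 95% CI in the analysis section. Assumed sex splits among the 54: 27/27, 32/22 and 35/19.

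**The plan's own figure.** 0.81 / √(1/18 + 1/36) = 0.81 / 0.289 = 2.806. Power = Φ(2.806 − 1.960) = 80.1% (noncentral t: 78.6%). The stated 0.81 is reproduced for the whole sample. The documents give no figure for balance or for the sex-specific analyses.

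**Chance of imbalance.** If allocation ignores sex, the number k in usual care from a sex with K members is hypergeometric: P(k) = C(K,k)·C(54−K,18−k) / C(54,18). The between-arm gap is k/18 − (K−k)/36 = (3k−K)/36.

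| Split | k giving a gap of at least 20 points | Probability |
|---|---|---|
| 27/27 | ≤6 or ≥12 | 14.8% |
| 32/22 (K = 32) | ≤8 or ≥14 | 14.8% |
| 35/19 (K = 35) | ≤9 or ≥15 | 13.6% |

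With 27/27, k ≤ 6 and k ≥ 12 each have probability 7.4%. Together they are the event that one sex has 6 or fewer usual-care participants instead of 9.

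**Cost of a bad draw.** In SD units, the standard error of one sex's effect is √(1/a + 1/b), with a in usual care and b in the intervention arm.
- 27/27, balanced, 9 v 18: 0.408.
- The short sex at 6 v 21: 0.463, a ratio of 1.13.
- The other sex is then 12 v 15: 0.387, a ratio of 0.95.
- 35/19, smaller sex: about 19/3 = 6.3 expected in usual care; P(4 or fewer) = 13%. At 4 v 15 the standard error is 0.563, against 0.494 at 6 v 13, a ratio of 1.14.

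**Average cost.** Weighting the standard error by P(k) and dividing by its value at exact 2:1 balance gives a mean increase of 1.4% for a sex of 27, 2.1% for the smaller sex of 22 and 2.8% for the smaller sex of 19.

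**What balance can achieve.** At 9 v 18, power for 0.81 is 48% and the 95% CI half-width is 0.84 SD. At 6 v 21 these are 39% and 0.95 SD.

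**Effect on the overall comparison.** If the two sexes differed by 0.5 SD in outcome (an assumption), a 20-point gap would move the unadjusted estimate by 0.20 × 0.5 = 0.10 SD; with 0.3 SD, by 0.06.

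**Does the remedy work?** A simulation of 2:1 minimisation (2,000 trials per setting) assumed three independent two-level factors and splits of 50:50 or 60:40 on the tracked factor. The preferred arm had probability 0.8 when it was usual care and 0.9 when it was intervention. The chance of a 20-point gap was about 15% with SIBDQ alone and 0.2% or less with sex and disease type added. Usual care still averaged about 18 people.

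**The case against.** The case against giving this much weight is good, and most of it stands.

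- The pilot's primary objective is feasibility and acceptability, the protocol says it is powered only for large differences, and the sex-specific estimates are additional analyses. Balancing the baseline value of a main outcome is a defensible choice.
- Subgroup size, not allocation, is the main limit on the sex-specific estimates. The 13% loss belongs to a tail draw and comes with a gain of about 5% for the other sex; the average loss is small.
- The plan does provide for imbalance in the overall comparison, through the clause on baseline variables that differ. For a 25-point gap in a 27/27 factor, adjustment raises the overall standard error by only about 3%. What remains is that the clause is data-driven, has no criterion and does nothing for the subgroup counts.

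Three stronger readings are tempting and are not supported:

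- A reader might infer bias from the omission. Allocation that ignores sex is as likely to err one way as the other, so this is chance imbalance.
- With a 35/19 split, the chance that the smaller sex has 6 or fewer in usual care is 54%, which sounds alarming. But 6 is the nearest whole number to the balanced expectation of 6.3, so the figure reflects the assumed split and the 2:1 ratio.
- A reader might put disease type on the same footing as sex. No effect analysis by disease type is planned, SIBDQ and the 0-10 symptom ratings are the same for both diseases, and the activity indices are listed as phenotype descriptors.

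**Conclusion.** The point holds for sex, at modest size. The plan splits its treatment effect by a factor that its allocation does not control, in an arm of 18. This leaves about a 14-15% chance of a gap of at least 20 points. The cost to one sex's standard error is about 13-14% in the bad draws worked above and about 1.4-2.8% on average. Adding sex guards mainly against the bad draw; the sex-specific estimates stay imprecise even when balanced.

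The figures rest on the assumed sex splits, on arms of exactly 36 and 18, and on sex being unrelated to the SIBDQ levels used in the minimisation. If the two are related, balancing SIBDQ also balances sex a little and the chances are somewhat lower. The counts are those at allocation; the Sample Size section aims for data on the same 54 and allows for no dropout, which could thin the groups further.

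**What to change.** 1. Add sex to the minimisation for all participants not yet allocated. Keep SIBDQ as a factor, include a random element, and count those already allocated in the running totals. The protocol records both sex and gender, so say which one defines the men and women of the analysis and use that one.
2. Prespecify sex as a covariate in the overall efficacy models, whether or not it is seen to differ between arms.
3. Optionally, treat disease type (Crohn disease v ulcerative colitis) in the same way; it can be taken from the medical record.

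The cost is a setting in the allocation program, a protocol amendment and slightly looser balance on SIBDQ, which the model adjusts for anyway. In April 2023, 4 of 54 participants had been enrolled, so at that date 50 could still have been allocated under the changed rule. If allocation has since finished, only the prespecified covariate remains available; it should be fixed before outcomes are compared by arm.
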